The proposed work is innovative because it aims to elicit the benefits of moral elevation to target trauma distress—a novel approach that is not currently used to treat Veterans, but is a promising area of research with significant support in other populations. We expect that OEF/OIF/OND Veterans will be able to complete this online intervention, and that their feedback will inform how to best implement moral elevation interventions in a Veteran population. Qualitative data will also be used to develop study methods for a future RCT to test the efficacy of a moral elevation intervention for targeting desired outcomes. Positive results from this study would indicate that this low-cost, web-based intervention could be easily disseminated to a wide range of Veterans and clinics, spanning from Veterans who are not actively engaged in care to those attending in-person treatment. Further, with replication, these findings could implicate moral elevation as a transdiagnostic tool that positively impacts complex psychological health needs (i.e., PTSD and MI), while also facilitating recovery through enhanced social functioning.

Keywords: web-based intervention, pilot study, moral elevation, veterans, PTSD, moral injury

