6.1 Methods Objectives

A 2-year pilot trial of a web-based elevation intervention for Veterans who experienced significant distress regarding a morally injurious event and with a current diagnosis of PTSD is proposed to assess: 1) feasibility of recruitment, retention, and completion of 8 sessions over a 1-month period; 2) ability of the intervention to elicit elevation; 3) acceptability of and satisfaction with elevation exercises, the intervention's general structure, and proposed methods; and 4) feasibility of randomization to a no-treatment condition to be used in future randomized controlled trials (RCTs) and completion of all assessments within this condition.

Participants will complete self-report measures that assess PTSD symptoms, MI distress, and social functioning as measured by prosocial behavior and quality of social relationships at baseline (BL; i.e., pre-intervention) and follow-up (FU; i.e., post-intervention). To supplement self-report measures and fully capture the potential impact on social functioning, each participant will invite 1 significant other (SO; e.g., spouse, friend) to complete measures based on observations of the Veteran's social behavior at baseline and follow-up. Veteran participants will be randomly assigned to an elevation intervention condition or a no-treatment control condition. Each condition comprises 2 web-based sessions per week (Monday and Thursday) for 1 month, totaling 8 sessions (<30 min/session).

Veteran participants will also complete repeated measures at each session, and Veterans in the intervention condition will complete an individual qualitative interview (~1 hr) with a qualified member of the study team at follow-up. The duration of the entire study for each Veteran participant is 6 weeks total. See Table 1 for a study timeline.

	Year	Pre		1			2	
	Quarte	Pre	12	2 3	8 4	1	2	34
Pre-Award Activities								
Obtain IRB approval; Hire psychology technician; Prepare online materials								
Training & Preparation								
Train psychology technician; Prepare recruitment/screening materials; Obtai eligible participants via VA CDW	n list of							
Conduct Pilot Study								
Telephone/eligibility screening assessment (n=5/month; total n=60)								
BL assessment & randomization (n=4/month; total n=48)								
8 online sessions (n=2/month; total n=24)								
FU assessment & qualitative interview* (n=2/month; total n=24) *Qualitative interview to be completed by treatment condition only								

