6.2 Participants

The targeted sample size for study completion is 24 Veterans, 12 per group.²⁵ Given that positive psychology web-based interventions have an average attrition rate of approximately 50% for clinical populations,²⁶ we aim to recruit and randomize 48 eligible Veterans within the initial baseline assessment to account for the expected attrition and to reach the goal of 24 Veteran completers. Specifically, "eligible" status is determined by passing the initial pre-screen over the phone, then passing the final screen for all inclusion and exclusion criteria after completion of the baseline assessment. For all Veterans who are determined eligible after the baseline appointment, one Significant Other will be recruited to complete observational measures for each Veteran. Therefore, we aim to recruit 48 eligible Veterans and 48 corresponding Significant Others. Given that participants need to verbally consent to the baseline appointment to determine final eligibility for full enrollment and randomization, it is possible that some consenting Veterans will not meet the inclusion criteria after consenting at baseline. In other words, consent does not automatically equal randomization. Any Veteran who consented but was then deemed ineligible based on the results of the baseline assessment would not be considered as contributing to the minimum sample size of 48 eligible Veterans. We anticipate that 2 out of every 3 participants is likely to be eligible after conducting a baseline appointment; therefore, we aim to obtain verbal consent from approximately 72 Veterans to meet the sample size required for eligible and enrolled Veterans. When combining the 48 Significant Others who are expected to consent after a Veteran is enrolled and randomized, we aim to recruit a total of 120 participants.

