6.3 Inclusion Criteria

Veteran Participants: Veterans must meet all of the following to participate: 1) \geq 18 years of age; 2) OEF/OIF/OND Veteran enrolled in CTVHCS; 3) English-speaking and able to provide written informed consent; 4) Internet access for web-based sessions and measures; 5) Screen positively for a PTSD diagnosis based on empirically-validated cutoffs on the PTSD Checklist for DSM-5 (PCL-5;²⁷ \geq 33); 6) Screen positively for experiencing \geq 1 morally injurious event and endorse some distress (\geq 4 on any distress item) related to that event based on the Moral Injury Events Scale (MIES);²⁸ 7) Willing to complete study procedures and identify a Significant Other who will complete observational measures; and 8) Willing to be randomized.

Significant Other Participants: Significant Others must meet all of the following to participate: 1) ≥ 18 years of age; 2) Designated as a Significant Other by the Veteran participant, and the Veteran participant has provided consent for the study team to contact that potential Significant Other; 3) English-speaking; 4) Internet access for web-based observational measures; 5) Interact with the Veteran ≥ 1 time per week; and 6) Willing to complete study procedures.

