Eligibility; SC = Sample Characteristics; SA = Specific Aim; RCT = Feasibility for use in
future RCT

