6.11 Statistical Analysis Plan

Aim 1.A: Assess the feasibility of recruitment, retention, and completion of an 8-session, 1month-long web-based moral elevation intervention.

Analysis Plan: The number and rates of Veterans screened and enrolled versus those retained through 8 sessions and the follow-up assessment will be examined. At all stages, efforts will be made to assess reasons for opting/dropping out to evaluate barriers to participating and feasibility of the proposed methods. The number of sessions completed for Veterans retained through 8 sessions will be examined.

Aim 1.B: Evaluate the ability of the intervention to elicit moral elevation.

Analysis Plan: Scores on the ES will be aggregated across several categories including each session (1-8), session type (video vs. life event recall), and the entire intervention. Mean scores >30, the mid-point of the ES (range=10-50), will be considered to adequately represent medium to high elevation responses to the exercises. We will conduct a visual inspection for trends in mean scores across session numbers and types, and for a signal that ES scores increase over time within each participant (i.e., trajectories across Sessions 1-8).

Aim 1.C: Assess the acceptability of and satisfaction with moral elevation exercises, the intervention's general structure, and the proposed methods.

Analysis Plan: Quantitative measures of acceptability and satisfaction ratings as measured by the TEI-SF and ESSS will be averaged across all participants in the intervention. Mean scores greater than the mid-point of each measure (TEI-SF=18; ESSS=22.5) will be considered trending in support of acceptability and satisfaction. Qualitative interviews will be transcribed. NVivo qualitative software will be used to organize and support coding of data. Methods of the intervention may be adapted immediately based on Veteran feedback if alternative approaches are needed to complete recruitment goals (e.g., retention problems).

Aim 2: Assess the feasibility of randomization to a no-treatment condition and completion of assessments at BL, repeated measures, and FU.

Analysis Plan: The number and rates of Veterans who were randomized to the no-treatment condition and retained through the FU assessment will be examined. The number of repeated measures completed (8 sessions) will also be examined.

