**Title: Pilot Study Testing a Web-Based Moral Elevation Intervention for
Veterans with PTSD and Moral Injury**

ID: D3035-P

NCT: NCT03906240

Principal Investigator: [name].

Statistical Analysis Plan

Date: 06.22.2021

Statistical Analysis Plan

All data management and analyses were conducted with R (R Core Team, 2021). To assess the feasibility and acceptability of MOVED, we calculated descriptive statistics for recruitment and retention data, self-report measures that focused on evaluating components of the intervention, and state elevation scores. For all evaluation measures, the mid-point score for a given measure was used as an indicator for adequate feasibility and acceptability (e.g., average/medium levels of acceptability, or higher). The mid-point score for state elevation was also used as an indicator for feasibility to induce elevation.

Qualitative interviews were transcribed, then coded using an inductive approach by two members of the research team and the first author. Two coders reviewed all transcriptions independently, identified codes based on interview responses, then met to discuss and modify codes. A consensus codebook was established and re-applied to all transcriptions. Emergent themes and subthemes were identified by the first author.

Preliminary examination of outcome measures was conducted via paired samples *t*-tests with the base stats package (`t.test`) and Cohen's *d* effect sizes within each condition with the `rstatix` package (Kassambara, 2021). Assessment of changes in pre-post measures included all participants who were randomized and provided post-session data.

References

- R Core Team. R: A language and environment for statistical computing. R Foundation for Statistical Computing [Internet]. 2021. Available from: <https://www.R-project.org/>
- Kassambara, A. `rstatix`: Pipe-Friendly Framework for Basic Statistical Tests [Internet]. 2021. Available from: <https://cran.r-project.org/web/packages/rstatix>

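### Outcome change is tested only within each arm; no between-arm estimate with an interval is planned, although the arms are randomised (minor)

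*SAP*

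**What the plan says.** Protocol section 6.1 sets the design: "Veteran participants will be randomly assigned to an elevation intervention condition or a no-treatment control condition". It also has Veterans report PTSD symptoms, moral injury distress and social functioning at baseline and follow-up.

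The only analysis of change in those outcomes is in the SAP: "Preliminary examination of outcome measures was conducted via paired samples" t-tests, plus Cohen's d within each condition. The analysis set is defined as follows: "Assessment of changes in pre-post measures included all participants who were randomized and provided post-session data".

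Protocol section 6.11 covers recruitment, retention, Elevation Scale scores, acceptability and completion. For the control arm it says: "The number and rates of Veterans who were randomized to the no-treatment condition and retained through the FU assessment will be examined". It gives no analysis of PTSD, moral injury or social outcomes.

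The purpose is limited. Section 5.1 states feasibility and acceptability aims, sets up the control arm to prepare for later randomised trials, and describes using qualitative data to "develop study methods for a future RCT to test the efficacy of a moral elevation intervention for targeting desired outcomes". The same section also offers the study as a source of pilot data for that later trial. The Table 2 legend (section 6.9) defines one purpose code as "RCT = Feasibility for use in" a future RCT.

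**The concern.** A later trial would test the difference between arms. The data collected here can give a rough estimate of that difference, but the plan stops at two separate within-arm changes. A paired pre-post test does not compare arms, whichever way the SAP sentence is parsed.

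Change within one arm mixes any intervention effect with influences that act in both arms. Section 6.4 lets Veterans start other treatment during the study. Both arms complete eight repeated assessments (sections 6.8 and 6.10). Entry also requires a raised PCL-5 score (section 6.3: "Screen positively for a PTSD diagnosis based on empirically-validated cutoffs on the PTSD Checklist for DSM-5"), so PTSD scores may fall by regression to the mean. Randomisation offsets such influences only if the arms are compared.

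At stake is the reading of the preliminary results. Someone planning the next trial could take a significant change in one arm and a non-significant change in the other as evidence of an effect, or carry a within-arm d forward as if it were a treatment effect.

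**Working it through.** **The plan's own figures.** Section 6.2 targets 24 completers (12 per arm) at about 50% attrition: 24/(1 − 0.5) = 48 randomised. With two in three eligible after baseline, 48/(2/3) = 72 consented; adding 48 Significant Others gives 120. All match. The documents state no alpha, effect size, SD or power for outcomes, so the inputs below are assumptions.

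**1. Risk of misreading two separate tests.** Assume two-sided alpha 0.05, normal change scores and the same true standardised change dz in both arms. Let p be the power of a paired t-test with n per arm (noncentral t, n − 1 df, noncentrality dz·√n). The arms are independent, so the chance of significance in the intervention arm only is p(1 − p). The SAP set is everyone randomised with post-session data, so n could lie anywhere from the 12 targeted to the 24 randomised per arm.

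| dz | p, n=12 | p(1 − p), n=12 | p, n=24 | p(1 − p), n=24 |
|---|---|---|---|---|
| 0.2 | 0.097 | 8.8% | 0.156 | 13.1% |
| 0.3 | 0.158 | 13.3% | 0.291 | 20.6% |
| 0.5 | 0.353 | 22.8% | 0.650 | 22.7% |
| 0.6 | 0.475 | 24.9% | 0.804 | 15.8% |
| 0.8 | 0.714 | 20.4% | 0.963 | 3.5% |
| 1.0 | 0.883 | 10.3% | 0.997 | 0.3% |

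In simulation at n = 12 (pre-post correlation r = 0.7, no selective dropout), a baseline-adjusted arm comparison rejects in 4.9% to 5.2% of trials over the same range.

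**2. Regression to the mean on the PCL-5.** Assume normal scores, a cut passing 50% to 84% of those screened (c = 0 to −1 in standard units), retest correlation 0.7 to 0.9 and no true change. Expected fall = (1 − r)·λ, with λ = φ(c)/(1 − Φ(c)).

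- Largest (c = 0, r = 0.7): 0.3 × 0.798 = 0.24 SD.
- Smallest (c = −1, r = 0.9): 0.1 × 0.288 = 0.03 SD.

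These are SDs of the unselected screened population. The SD after truncation is √(1 − λ(λ − c)): 0.603 at c = 0 and 0.794 at c = −1. In SDs of the enrolled sample the range is therefore 0.029/0.794 = 0.04 to 0.239/0.603 = 0.40.

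Two points limit this.

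- The PCL-5 is given at the phone screen (section 6.6). Section 6.2 describes eligibility as "then passing the final screen for all inclusion and exclusion criteria after completion of the baseline assessment", but section 8.2 A.1 names only exclusion criteria for the final screen, so a repeat PCL-5 cut at baseline is inferred. Without one, part of the fall happens before baseline.
- Table 2 codes the PCL-5 for eligibility. Sections 6.1 and 8.1 B say PTSD symptoms are measured as study data, but the SAP names no outcome scale.

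**3. Precision of an arm comparison.** 95% half-width for ANCOVA = t(0.975, 2n − 3)·√((2/n)(1 − r²)), in SDs of the score.

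| r | n=12 (t = 2.080) | n=24 (t = 2.014) |
|---|---|---|
| 0.5 | 0.74 | 0.50 |
| 0.7 | 0.61 | 0.42 |
| 0.8 | 0.51 | 0.35 |

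Chance baseline imbalance widens these slightly.

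**4. Effect of dropout.** Illustration: 24 per arm randomised, about 50% retained, no true change, and selective dropout in one arm only (odds ratio 2.7 per SD of the driving score); 8,000 simulated trials per setting.

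| Dropout depends on | r | Error in that arm's mean change (SD) | Error in ANCOVA (SD) | ANCOVA rejects |
|---|---|---|---|---|
| baseline | 0.5 | 0.20–0.21 | under 0.01 | about 5% |
| baseline | 0.7 | 0.12–0.13 | under 0.01 | about 5% |
| follow-up | 0.5 | 0.20–0.21 | 0.30–0.32 | 13–14% |
| follow-up | 0.7 | 0.12–0.13 | 0.21–0.22 | 10–11% |

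The 5% rejection rate therefore holds only when dropout does not depend on the follow-up score.

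**The case against.** This is a feasibility pilot, and none of its stated aims needs an arm contrast. The control arm is analysed for retention and completion, efficacy is left to a later trial, and the SAP calls the outcome work preliminary. Control-arm change is reported beside intervention change, so a crude comparison is visible. The contrast would be imprecise and, under follow-up-dependent dropout, further off than the within-arm mean change. The SAP is also written in the past tense, so the remedy would be an added exploratory estimate.

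All of this stands, and it limits the weight. It does not remove the point: the SAP itself chooses to run significance tests on outcomes, and section 5.1 offers the study as pilot data for a trial of the arm difference. Two mean changes placed side by side give no interval and no baseline adjustment.

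A reader might infer more than the documents support:

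- That the plan will claim efficacy from within-arm p-values. Neither document says those p-values will be compared, or that the outcome effects will size the next trial.
- That regression to the mean affects all outcomes. The calculation concerns the PCL-5. For moral injury it is at most indirect, because entry uses the MIES while the scale coded for a future RCT is the EMIS-M.
- That baseline adjustment cures attrition bias. It does not, as the dropout illustration shows.

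**Conclusion.** The point holds as a minor one about analysis and reporting. No between-arm estimate with an interval is planned for outcomes that are measured in both randomised arms and tested for change.

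The misreading pattern is common for small to moderate shared changes at either sample size (about 9% to 23% for dz 0.2 to 0.5). For large shared changes it depends strongly on n: at dz 0.8 it is about 20% with 12 per arm and 3.5% with 24. These rates assume two-sided alpha 0.05, normal changes and equal true change in both arms.

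Regression to the mean is plausible for PTSD symptoms if the PCL-5 is the outcome measure, at 0.04 to 0.40 SD of the enrolled sample under the assumptions shown.

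A reader might conclude that the trial fails its purpose. It does not: recruitment, retention, elevation and acceptability results are untouched. The case for an arm comparison rests on using the randomisation, not on better handling of missing data.

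**What to change.** For each outcome, name the scale and add one exploratory baseline-adjusted between-arm difference with a 95% confidence interval. ANCOVA among those with follow-up or a constrained-baseline mixed model would each serve. State that it assumes follow-up is missing at random given baseline and arm, and report baseline scores by arm for those with and without follow-up.

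Keep within-arm change and d as description. Say that no efficacy inference is intended and that the two within-arm p-values do not compare the arms. If analysis has already been done, label the estimate as a later addition.

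The cost is a few sentences in the SAP and a few lines of R. The downside is that the intervals will be wide, and the estimate may mislead if those who do badly or well at follow-up are the ones lost. Both should be stated beside the result.

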Analyses								
Analyses of qualitative data; Analyses of recruitment & retention data								
Formulate future research (RCT grant proposal) based on results								
Disseminate results via national academic conferences & scientific journals								

Table 1. Study Timeline, Procedures, and Recruitment Goals

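### Unadjusted paired t-tests and a within-arm Cohen's d, on about 12 completers per arm and with no between-arm contrast, are neither evidence of benefit nor a sound planning effect for the RCT

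*SAP*

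**What the plan says.** The SAP's only analysis of outcome change is one short paragraph: "Preliminary examination of outcome measures was conducted via paired samples" t-tests, with Cohen's d "effect sizes within each condition". The analysis set "included all participants who were randomized and provided post-session data". The paragraph does not list the outcomes, name a primary one, or give an alpha, a multiplicity rule, a confidence interval, the SD used in d, or a comparison between arms. Protocol 6.11 does not fill these gaps, because it contains no analysis of outcome change.

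On numbers, Protocol 6.2 says "The targeted sample size for study completion is 24 Veterans, 12 per group". It cites an "average attrition rate of approximately 50% for clinical populations", and therefore "we aim to recruit and randomize 48 eligible Veterans within the initial baseline assessment".

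On use, Protocol 5.1 describes the study as a source of pilot data for a later trial, and Table 1 in Protocol 6.1 schedules this step: "Formulate future research (RCT grant proposal) based on results".

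**The concern.** Many small tests without an error rule make an isolated significant change easy to obtain by chance, while real moderate changes will often be missed. At this size a p-value tells the reader little either way.

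The effect size has a separate problem. A within-arm d contains everything that moves scores between baseline and follow-up, not only the intervention. Veterans are selected on PCL-5 of at least 33 (Protocol 6.3), so some fall in that score is expected from regression to the mean. They may also start other treatment during the study (Protocol 6.4). The trial randomizes a no-treatment arm that would show this background change, but the SAP never subtracts it. What is at stake is over-reading of the pilot, and an RCT proposal that takes its outcomes or its planning effect from these figures.

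**Working it through.** **Plan's own figure.** 24 completers / (1 − 0.50) = 48 randomized, as stated. If allocation is 1:1 (implied by 12 completers per group), that is 24 randomized and 12 completing per arm.

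**Number of tests (a count; the plan states none).** Table 2 in Protocol 6.9 marks these for RCT use: EMIS-M, WHOQOL-BREF, PANAS-SF, PANSE, RPA, CG and PS from the Veteran (7), and PS and IMI from the Significant Other (2). Protocol 6.1 says that PTSD symptoms are measured at baseline and follow-up, which adds the PCL-5.
- Veteran-reported only: 8 × 2 arms = 16 tests.
- With the two observer scales: 10 × 2 arms = 20 tests.
- Separate subscale tests would raise the count.

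**Chance of at least one false positive.** Assumptions: two-sided 0.05, no adjustment, no true change in any measure. For m independent tests it is 1 − 0.95^m:
- m = 16: 1 − 0.95^16 = 0.56
- m = 20: 1 − 0.95^20 = 0.64, with 20 × 0.05 = 1 false positive expected

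For correlated outcomes, simulation (two independent arms, n = 12 each, equal correlation among change scores) gives:

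| Correlation | 16 tests | 20 tests |
|---|---|---|
| 0.3 | 52% | 58–59% |
| 0.5 | 45% | 51% |
| 0.7 | 37% | 40% |

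For the intervention arm alone (10 tests) the figures are 40% if independent, 30% at correlation 0.5 and 23% at 0.7.

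**Power.** Paired t-test, d = 0.5 in SDs of change. At n = 12: df 11, noncentrality 0.5 × √12 = 1.73, power 35%. At n = 24, the most possible with no attrition: 65%.

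**Precision.** The half-width of the 95% interval for mean change is t(0.975, 11)/√12 = 0.64 SD of change. The same number is the smallest |d| that reaches p < 0.05 at n = 12. An observed d of 0.5 has a 95% interval of −0.11 to 1.09 at n = 12, and 0.07 to 0.92 at n = 24.

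**Small-sample bias.** The Hedges factor at 11 df is 1 − 3/(4 × 11 − 1) = 1 − 3/43 = 0.930, so the correction lowers d by about 7%.

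**Ignoring control change (illustration).** For 80% power at two-sided 0.05, a between-arm d of 0.5 needs 63 per arm. If the intervention arm changes by 0.5 but half of that also occurs without treatment, the between-arm d is 0.5 − 0.25 = 0.25, and the need is 252 per arm, four times as many. The one-half is an assumption; the documents give no figure for control change.

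**The case against.** The best defence is that the analysis is labelled preliminary and nothing in the pilot depends on it. Feasibility and acceptability are judged by recruitment, retention and scale mid-points. That stands, and it limits the harm to over-interpretation.

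Four stronger readings are tempting, and the documents do not support them.

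- *A chance finding is likely.* 64% needs 20 independent tests at 0.05 with every null true. These outcomes overlap in content, and with correlation of 0.7 the chance is 40% or a little less.
- *Twenty tests on Veterans.* The SAP gives no count, and two of the ten measures are completed by Significant Others. Table 2 tags the PCL-5 for eligibility only, so counting it relies on Protocol 6.1. The table's timing marks could not be read in the text reviewed.
- *A paired d would make the RCT 1.7 to 2.5 times too small.* This needs three things at once: a d standardised by the SD of change, a pre-post correlation r of 0.7 to 0.8, and an RCT that compares raw follow-up scores. The documents establish none of them. Paired d equals the score-SD d times 1/√(2(1 − r)), which is 1.00 at r = 0.5 and 0.85 at r = 0.3. For an RCT that compares change scores, change divided by the SD of change is the right scale. For a score-SD d of 0.5, sizing on the paired d gives 38 per arm (r = 0.7) or 26 (r = 0.8). Baseline-adjusted ANCOVA would need about 63 × (1 − r²), or 32 and 23, so the trial would be slightly oversized.
- *The within-arm d will size the RCT.* No section says so. Protocol 5.1 and Table 1 say only that the results feed the next trial. Neither document rules that use out.

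**Conclusion.** The concern holds as a reporting and planning weakness, not as a flaw in the pilot's stated aims. The missing outcome list, alpha, multiplicity rule, interval and between-arm contrast are plain from the SAP. The 40% to 64% (37% for 16 tests at correlation 0.7) rests on the count of 16 to 20 tests, an assumed 0.05 and no true change. The 35% power and ±0.64 SD rest on the target of 12 per arm and ease if attrition is below 50%. The objection to a within-arm d rests on none of these assumptions, because it cannot separate the intervention from background change at any sample size. The change is worth making because planning an RCT is a declared purpose of the study and the cost is small.

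**What to change.** Replace the p-values with estimates. Multiplicity adjustment is a poor alternative: Bonferroni over 20 tests (0.0025 each) would need |d| of at least 1.12 at n = 12.

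In the SAP:
1. List the pre-post outcomes and the rater for each.
2. For each measure and arm, report mean change, its SD, the baseline SD, the pre-post correlation and a 95% interval for the change.
3. Add the between-arm difference in change with a 95% interval. It will be wide: at 12 per arm, a between-arm d of 0.5 carries about 1.96 × √(2/12 + 0.25/48) = ±0.81.
4. State which SD standardises d, and apply the Hedges correction. Reporting both SDs and the correlation lets RCT planners convert to the scale that their analysis needs.
5. State that these figures are exploratory and not evidence of efficacy.

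The cost is SAP wording and a few lines of R, with no new data. The results may look less favourable. The SAP is written in the past tense; if the tests have already been run, the same changes can be made in the report.
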